9.4.2. Secondary Efficacy Endpoints

The secondary endpoints and estimands are described in Section 3. Estimands for changes in OCS use will use the subpopulation of participants with HES aged 6 to 17 years that are taking OCS at baseline. An additional estimand for changes in OCS use will use the whole population of participants with HES aged 6 to 17 years. The secondary estimand for fatigue severity will use the subpopulation of participants with HES aged 12 to 17 years.

All secondary efficacy endpoints will be summarised descriptively. For the estimands for changes in OCS use, a treatment policy strategy will be used for the intercurrent events of discontinuation of study medication. For these estimands, use of OCS is part of the endpoint (composite strategy). Other changes in background HES medication will use a treatment policy strategy. For the secondary estimand for fatigue severity a treatment policy strategy will be used for the intercurrent events of discontinuation of study medication and change in background HES medication.

For the following dichotomous secondary endpoints, participants withdrawing prematurely from the study who have no available data during Weeks 48 to 52 will be summarised as not having met the endpoint criteria i.e., a treatment failure:

- Reduction of $\geq 50\%$ in mean daily OCS dose (prednisone/prednisolone or equivalent) from Weeks 0 to 4 compared with Weeks 48 to 52 in participants that are taking OCS at baseline
- Achieving a mean daily OCS dose (prednisone/prednisolone or equivalent) of ≤ 7.5 mg during Weeks 48 to 52 in participants that are taking OCS at baseline
- Achieving a mean daily OCS dose (prednisone/prednisolone or equivalent) of ≤ 7.5 mg during Weeks 48 to 52

For all other secondary endpoints, available data up to the time of study withdrawal will be summarised.

CCI

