4.3. Secondary Efficacy Endpoint Analyses

All secondary endpoints will be summarised descriptively. Each four-week period from Weeks 0-4 through to Weeks 48-52 is shown in Section 6.2.4.2.

4.3.1. Change in the mean daily OCS dose (prednisone/prednisolone or equivalent) from Weeks 0 to 4 to Weeks 48 to 52

Derivation of Endpoint

For each participant, the OCS dose on each day of the study will be identified from the concomitant medications data (see Section 6.2.1). The mean daily OCS (prednisone or equivalent) dose for each 4-week period (Weeks 0-4 through to Weeks 48-52) for each participant will be calculated as the sum of the daily doses of OCS during each period divided by the total number of days (see Section 6.2.1.1).

Participants withdrawing from the study prematurely will have mean daily OCS (prednisone or equivalent) dose calculated using available data up to study withdrawal date only (divided by the number of days for which there is available data).

The change in the mean daily OCS dose from Week 0 to 4 to Week 48 to 52 will be calculated for each participant as the mean daily OCS dose for Week 48 to 52 minus the mean daily OCS dose for Week 0 to 4. The change in the mean daily OCS dose from Week 0 to 4 to each 4-week period from Weeks 4-8 through to Weeks 48-52 will be calculated using the same formula.

The estimand for this endpoint is described in Section 1.1 and summarised below.

Target Participant Population	Participants with HES aged 6 to 17 years that are taking OCS at baseline, i.e. mean Week 0 to 4 OCS dose >0 mg/day.
Endpoint	Change in the mean daily OCS dose (prednisone/prednisolone or equivalent) from Weeks 0 to 4 to Weeks 48 to 52.
Intercurrent events	The anticipated intercurrent events and corresponding strategies are:- 
 • Study treatment discontinuation: treatment policy strategy. • Changes to OCS therapy: composite strategy (part of endpoint). • Other changes to background HES medication which might modulate the disease course of HES, determined either by published data or by proposed or known mechanism of action: treatment policy strategy.
Summary measure	Mean change from Weeks 0 to 4 to Weeks 48 to 52 across participants.

Main analytical approach

Summary statistics for mean daily OCS (prednisone or equivalent) dose for each 4-week period from Weeks 0-4 through to Weeks 48-52 will be presented by treatment group, including change in the mean daily OCS dose.

Additional Estimands

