An additional estimand for this endpoint will use the whole population of participants with HES aged 6 to 17 years.

4.3.2. Reduction of $\geq 50\%$ in mean daily OCS dose (prednisone/prednisolone or equivalent) from Weeks 0 to 4 compared with Weeks 48 to 52

Derivation of Endpoint

Participants who achieve a mean daily OCS dose (prednisone/prednisolone or equivalent) reduction of 50% or more from Week 0-4 to each 4-week period from Weeks 4-8 through to Weeks 48-52 will be determined based on the change in mean OCS dose defined in Section 4.3.1. For each 4-week period a reduction of 50% or more is defined as:

$$\frac{\text{Mean OCS dose} - \text{Mean OCS dose during Week 0 to 4}}{\text{Mean OCS dose during Week 0 to 4}} \times 100 \leq -50$$

The estimand for this endpoint is described in Section 1.1 and summarised below.

Target Participant Population	Participants with HES aged 6 to 17 years that are taking OCS at baseline, i.e. mean Week 0 to 4 OCS dose >0 mg/day.
Endpoint	Reduction of ≥50% in mean daily OCS dose (prednisone/prednisolone or equivalent) from Weeks 0 to 4 compared with Weeks 48 to 52.
Intercurrent events	The anticipated intercurrent events and corresponding strategies are:- 
 • Study treatment discontinuation: treatment policy strategy. • Changes to OCS therapy: composite strategy (part of endpoint). • Other changes to background HES medication which might modulate the disease course of HES, determined either by published data or by proposed or known mechanism of action: treatment policy strategy.
Summary measure	Proportion of participants with reduction of ≥50% in mean daily OCS dose (prednisone/prednisolone or equivalent) from Weeks 0 to 4 compared with Weeks 48 to 52.

Main Analytical Approach

The number and percentage of participants who achieve a reduction in mean daily OCS (prednisone/prednisolone or equivalent) dose of 50% or more during Week 48 to 52 will be presented by treatment group. The number and percentage of participants who achieve a reduction in mean daily OCS dose of 50% or more during each 4-week period from Weeks 0-4 to each 4-week period from weeks 4-8 through to Weeks 48-52 will also be tabulated.

Participants withdrawing prematurely from the study who have no available data during Weeks 48 to 52 will be summarised as not having met the endpoint criteria, i.e., a treatment failure. The same approach will be used for the summary for each of the other 4-week periods.

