For participants withdrawing prematurely from the study, available data up to the time of study withdrawal will be summarised.

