6.2.4.2. Medication Assessment Windows

For the reporting of medication use and changes in medication use (e.g. change in OCS dose and change in immunosuppressive and/or cytotoxic HES therapy) will be assigned to a 4-weekly analysis time point according to the table below.

Table 4 Medication Assessment Windows

Reporting Period	First Day Included	Last Day Included
Pre-treatment	Medication is taken on the date of first dose of IP (Day 1)	
Weeks 0-4 (Baseline)	Day after day of first dose	28 days after day of first dose
Weeks 4-8	29 days after day of first dose	56 days after day of first dose
Weeks 8-12	57 days after day of first dose	84 days after day of first dose
Weeks 12-16	85 days after day of first dose	112 days after day of first dose
Weeks 16-20	113 days after day of first dose	140 days after day of first dose
Weeks 20-24	141 days after day of first dose	168 days after day of first dose
Weeks 24-28	169 days after day of first dose	196 days after day of first dose
Weeks 28-32	197 days after day of first dose	224 days after day of first dose
Weeks 32-36	225 days after day of first dose	252 days after day of first dose
Weeks 36-40	253 days after day of first dose	280 days after day of first dose
Weeks 40-44	281 days after day of first dose	308 days after day of first dose

Reporting Period	First Day Included	Last Day Included
Weeks 44-48	309 days after day of first dose	336 days after day of first dose
Weeks 48-52	337 days after day of first dose	364 days after day of first dose

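### Participants who withdraw with no final-window data drop out of the mean OCS change and mean BFI item 3 change, although the estimands cover them and the OCS responder endpoints count them as failures

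*SAP*

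**What the plan says.** **OCS mean change (SAP 4.3.1).** The target population is everyone with a Weeks 0-4 mean OCS dose above 0 mg/day, and treatment discontinuation is handled by treatment policy. For early withdrawers the mean dose is "calculated using available data up to study withdrawal date only", with the number of observed days as divisor. The endpoint is "the mean daily OCS dose for Week 48 to 52 minus the mean daily OCS dose for Week 0 to 4". In SAP 6.2.4.2 the last window opens "337 days after day of first dose" and closes at 364 days.

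**BFI item 3 (SAP 4.3.4).** The target population is all participants aged 12 to 17 years, again with treatment policy. The Week 52 value averages the diary scores from the seven days before the Week 52 clinic visit. The withdrawal rule reads: "For participants withdrawing prematurely from the study, available data up to the time of study withdrawal will be summarised".

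**Protocol 9.4.2.** After listing the dichotomous OCS endpoints, it states: "For all other secondary endpoints, available data up to the time of study withdrawal will be summarised".

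**OCS responder endpoints (SAP 4.3.2 and 4.3.3).** Early withdrawers "who have no available data during Weeks 48 to 52 will be summarised as not having met the endpoint criteria". Protocol 9.4.2 has the same rule.

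**Sensitivity analysis.** The only one for missing data is in SAP 4.2.3. It concerns flares and depends on there being enough off-treatment data. SAP 4.3.1 and 4.3.4 contain none.

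**The concern.** Each estimand names a whole population, but the stated rule averages only those with a value in the final window. For OCS the plan takes two views of the same withdrawal. The responder proportions keep the participant as a failure, while the mean change, computed from the same dose records, leaves the participant out. The two OCS results would then sit side by side on different denominators.

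If participants leave because the disease is poorly controlled, the remaining mean is more favourable than the mean over the population named in the estimand. The groups are small: at least 15 participants in all, with a planned minimum of 4 adolescents (SAP version history and Protocol Amendment 04 summary). One loss can visibly move a mean. Protocol 2.3.2 says the results are meant to support an EMA submission.

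**Working it through.** The plan gives no figure on this point to reproduce. Its one precision statement, a 95% CI of 0.07 to 0.93 for a flare rate of 0.26/year, concerns the primary endpoint and plays no part here.

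**Step 1: who has a value.**
- *OCS.* The window has 364 - 337 + 1 = 28 days. With no observed day in it there is no Weeks 48-52 mean, so the difference cannot be formed. With at least one observed day, SAP 4.3.1 averages the days available.
- *BFI.* The Week 52 window is counted back from the Week 52 visit date (SAP 4.3.4 and Table 3), so without that visit there is no anchor. SAP 6.2.4 moves early-withdrawal-visit data to the next scheduled visit. That does not give an earlier withdrawer a Week 52 value, and the SAP does not say how daily diary scores are windowed when the Week 52 visit is missing.
- *Treatment discontinuers.* Under Protocol 7.1 they continue to Week 52 where possible, with the eDiary, and so enter both means.

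**Step 2: size of the difference.** Let n be the estimand population, k the withdrawers with no final value, and m the mean change in the other n - k. If the withdrawers had zero change, the full mean is m(n - k)/n. The available-data mean exceeds it by the factor n/(n - k), an overstatement of k/(n - k).

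| Endpoint | n | k | Share lost, k/n | Overstatement, k/(n-k) |
|---|---|---|---|---|
| BFI | 4 | 1 | 25% | 1/3 = 33% |
| OCS | 8 | 1 | 12.5% | 1/7 = 14% |
| OCS | 10 | 1 | 10% | 1/9 = 11% |
| OCS | 15 | 2 | 13.3% | 2/13 = 15% |

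Only the 4 adolescents (a planned minimum) and the 15 participants (the planned total, so an upper case for OCS users at that sample size) come from the documents. The number on OCS at baseline and every k are assumed.

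**Step 3: an illustration in dose units (all inputs assumed).** Take 10 OCS users, of whom 2 withdraw before Week 48, and 6 of the 8 who stay respond.
- Responder result: 6/10 = 60%, against 6/8 = 75% among those with data.
- Mean change of -6.0 mg in the 8. Over all 10 it is (8 x -6.0 + 2 x 0)/10 = -4.8 mg with zero change in the two withdrawers, and (8 x -6.0 + 2 x 5)/10 = -3.8 mg if each rose by 5 mg.
- For BFI, a mean of -2.0 in 3 adolescents becomes (3 x -2.0 + 0)/4 = -1.5 over 4.

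**Step 4: how likely.** The chance of at least one withdrawal is 1 - (1 - p)^N, with independent withdrawals. At assumed rates p of 5%, 10% and 20% it is 54%, 79% and 96% among 15, and 19%, 34% and 59% among 4. With no withdrawal before the final window, the issue does not arise.

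**Step 5: a related inconsistency.** SAP 6.2.1.1, to which 4.3.1 refers, divides the window total by a fixed 28. For someone on 10 mg/day observed for 7 days of the window, 4.3.1 gives 70/7 = 10 mg/day and 6.2.1.1 gives 70/28 = 2.5 mg/day. Read literally, 6.2.1.1 gives a participant with no days in the window 0/28 = 0 mg, an apparent full reduction. Steps 1 to 3 take 4.3.1 as governing, because it is the text that addresses withdrawers.

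**The case against.** The strongest reply is that the design already limits the problem. Participants who stop mepolizumab are asked to remain to Week 52, and their data enter both means. Those who leave the study forfeit the expanded access program, while discontinuers who stay can still be considered (Protocol 6.6). Protocol 9.4.1 expects little missing data, though it says so of the primary endpoint. All secondary results are descriptive. SAP 4.1.1 already reports n for continuous summaries, SAP 6.1.1 tabulates withdrawals with reasons, and OCS change and BFI are shown for every earlier period, so withdrawers' earlier data appear. Scoring missing as failure also has no automatic counterpart for a mean.

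Most of this stands and limits the weight of the point. It does not remove it: reporting n shows that people are missing but not how far the mean could move, and no visible analysis of the two means does so.

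A reader might infer more than the documents support:
- *That the means cover completers only, or omit every withdrawer.* Protocol 4.4 defines completion by the Week 52 visit. Someone who leaves during Weeks 48-52 is not a completer, yet contributes observed days to the OCS mean.
- *That BFI shows the same inconsistency.* The failure rule concerns OCS dose. A participant leaving at Week 50 can lack a Week 52 BFI value without being an OCS failure. For BFI the gap is only between estimand population and available data.
- *That protocol and SAP conflict.* The different handling is set out in Protocol 9.4.2, and the SAP follows it.

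**Conclusion.** The point holds in a limited form. Under the available-data rule, participants who withdraw with no Weeks 48-52 dose data, or no Week 52 BFI window, are absent from means whose estimands include them. For OCS, the responder endpoints treat the same people as failures.

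With zero change in withdrawers the overstatement is k/(n - k), about 33% for 1 of 4 adolescents and 14% for 1 of 8 OCS users. These figures rest on assumed withdrawals, an assumed number of OCS users and the zero-change assumption. A reader might infer that bias towards benefit is established. It is not: the documents give no withdrawal rate and no expected reasons for withdrawal, and withdrawal unrelated to disease control need not bias the mean in either direction.

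The primary endpoint is unaffected, and with no hypothesis test no error rate is at stake. The issue is how two descriptive means can be read, and it is worth settling because the remedy is cheap.

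**What to change.** In SAP 4.3.1 and 4.3.4, keep the available-data mean as the main summary. Add one supplementary row over the full estimand population, in which withdrawn participants with no Weeks 48-52 data (OCS) or no Week 52 value (BFI) are given zero change. Label it a conservative sensitivity check, not an estimate of the treatment-policy mean, and show n and N for both rows. Then the OCS mean change can be read beside the responder proportions on a common denominator.

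In the same edit, state that the days-observed divisor in 4.3.1 governs over the fixed 28 in 6.2.1.1 for withdrawers, and that a window with no observed days gives a missing value.

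The cost is a few sentences and one extra row in two descriptive tables. The supplementary figure may be slightly less favourable, and assigning a single value understates its SD, so the available-data SD should stay alongside.

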5.1. Inclusion Criteria

Participants are eligible to be included in the study only if all of the following criteria apply:

Age

1. Participant must be aged 6 to 17 years inclusive, at Screening (Visit 1).

Type of Participant and Disease Characteristics

2. Participants who have been diagnosed with **HES for at least 6 months** prior to enrolment (Visit 2). HES diagnosis is based on signs or symptoms of organ involvement and/or dysfunction that can be directly related to:
 - Blood eosinophilia of >1500 eosinophils/ μ L on at least 2 occasions, and/or
 - Tissue eosinophiliadocumented prior to Visit 2 without a discernible non-haematological secondary cause (e.g., drug hypersensitivity, parasitic infection, human immunodeficiency virus [HIV] infection, non-haematological malignancy).

Tissue eosinophilia is defined as a history of 1 or more of the following:

- The percentage of eosinophils exceeds 20% of all nucleated cells in bone marrow sections
- In the opinion of a pathologist, tissue infiltration by eosinophils is extensive (massive) when compared with the normal physiologic range, compared with other inflammatory cells, or both

- A specific stain directed against an established eosinophil granule protein (e.g., major basic protein) reveals extensive extracellular deposition of eosinophil-derived proteins indicative of local eosinophil activation [Valent, 2012].
3. A history of 2 or more HES flares within the past 12 months prior to Screening (Visit 1). Historical HES flares are defined as documented HES-related worsening of clinical symptoms or blood eosinophil counts requiring an escalation in therapy. At least one HES flare within the past 12 months must not be related to a decrease in HES therapy during the 4 weeks prior to the flare.
 4. Participants must have blood eosinophil count ≥ 1000 cells/ μ L present at Screening.
 5. Participants must be on a stable dose of HES therapy for the 4 weeks prior to the first dose of mepolizumab (Visit 2). HES therapy includes but is not limited to OCS, immunosuppressive, and cytotoxic therapy. Participants who are not on maintenance therapy during this period are eligible if they meet other criteria.

Sex and Contraceptive/Barrier Requirements

6. Male and/or female [(according to their reproductive organs and functions assigned by chromosomal complement)] [FDA, 2016].

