8.1.1. HES Flare

A HES flare is defined as a HES-related clinical manifestation based on a physician documented change in clinical signs or symptoms (worsening symptoms and/or elevated blood eosinophil level) resulting in the need for either of the following:

- An increase from the most recent dose in the maintenance OCS dose (prednisone/prednisolone equivalent) by at least 10 mg/day for 5 days
- An increase in or addition of any immunosuppressive and/or cytotoxic HES therapy from/to the most recent dose of HES therapy.

To be considered as a HES flare, the most recent dose of HES therapy must not have changed for at least 4 weeks prior to the flare. This ensures that failed reductions in HES therapy are not misclassified as a HES flare.

The start date for a HES flare will be defined as the date of therapy escalation confirmed by the investigator attributable to a HES-related clinical manifestation.

When a participant experiences a HES flare, the investigator will monitor the change in disease control per routine medical care (e.g., follow-up call) and record the resolution of the flare including the end date. Investigators are encouraged, as medically appropriate, to return the participant's treatment regimen to the level prior to the flare after the flare has resolved.

In the event of disease worsening for which the investigator suspects a HES flare between scheduled clinic visits, when possible, the participant will return to the clinic to have the unscheduled 'Flare' visit assessment completed as described in the SoA. When attending the clinic visit at the time of a suspected HES flare is not possible, the investigator should make every effort to evaluate the participant via telephone and complete the CCI [REDACTED]. If an escalation of therapy is initiated by a non-study physician, the investigator should confirm that the escalation in therapy is attributable to a HES-related clinical manifestation.

CCI

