4.2.1. Definition of endpoint/estimands

Definition of HES flare:

A HES flare is defined as a HES-related clinical manifestation based on a physician documented change in clinical signs or symptoms (worsening symptoms and/or elevated blood eosinophil level) resulting in the need for either of the following:

- An increase from the most recent dose in the maintenance OCS dose (prednisone/prednisolone equivalent) by at least 10 mg/day for 5 days.
- An increase in or addition of any immunosuppressive and/or cytotoxic HES therapy from/to the most recent dose of HES therapy.

To be considered as a HES flare, the most recent dose of HES therapy must not have changed for at least 4 weeks prior to the flare. This ensures that failed reductions in HES therapy are not misclassified as a HES flare.

The start date for a HES flare will be defined as the date of therapy escalation confirmed by the investigator attributable to a HES-related clinical manifestation.

Derivation of Endpoint

HES flares are recorded by the investigators in the HES flares details form. The number of observed HES flares will be calculated for each participant as the number of unique starting dates for HES flares which occur at least 14 days after the date of resolution from any preceding HES flare. Both on- and off-treatment flares will be included within the analysis of the primary endpoint, however any post-treatment flares recorded will not be included (see Section 6.2.2.1).

Primary Estimand

The primary estimand is described in Section 1.1 and summarised below.

Target Participant Population	Participants with HES aged 6 to 17 years with or without maintenance SoC therapy.
Primary Endpoint	Frequency of HES flares over 52 weeks.
Intercurrent events	The anticipated intercurrent events and corresponding strategies are:- 
 • Study treatment discontinuation: treatment policy strategy. • Change to background HES medication which might modulate the disease course of HES, determined either by published data or by proposed or known mechanism of action (other than changes due to a clinically documented flare): treatment policy strategy.
Summary measure	Annualised rate of HES flares.

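### The 'taking OCS at baseline' subgroup, and the reference dose for two OCS endpoints, are set from the 28 days after first dose, so an early OCS-treated flare can select participants and read as a later dose reduction

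*SAP*

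**What the plan says.** There are four OCS secondary endpoints (Protocol Section 3 and 8.1.3; SAP 1.1). Three are for participants on OCS at baseline: change in mean daily dose, a reduction of at least 50%, and a mean dose of 7.5 mg or less in Weeks 48-52. The fourth applies the 7.5 mg threshold to everyone.

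SAP 4.3.1, 4.3.2 and 4.3.3 define the target population of the first three as participants "taking OCS at baseline, i.e. mean Week 0 to 4 OCS dose >0 mg/day". The change is the "mean daily OCS dose for Week 48 to 52 minus the mean daily OCS dose for Week 0 to 4", and the 50% criterion divides that change by the same Weeks 0-4 mean.

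SAP Table 4 (6.2.4.2) labels the window "Weeks 0-4 (Baseline"). It starts the day after the first dose and ends "28 days after day of first dose". OCS taken on Day 1 sits in a separate pre-treatment row that none of these formulas uses.

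The protocol itself names Weeks 0 to 4 as the reference for the change and 50% endpoints. Its visible text does not say how being on OCS at baseline is determined. That step appears in the SAP and is not listed in SAP 4.11.

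One of the two routes to a flare is "An increase from the most recent dose in the maintenance OCS dose (prednisone/prednisolone equivalent) by at least 10 mg/day for 5 days" (SAP 4.2.1; same rule in Protocol 8.1.1). SAP 6.2.2.1 counts flares from the date of first dose.

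**The concern.** A subgroup labelled by baseline status should not depend on what happens after treatment starts. Here it can. Participants on no maintenance therapy are eligible (Protocol 5.1, inclusion 5). If one of them has an OCS-treated flare in the first four weeks, the Weeks 0-4 mean exceeds zero and the participant joins the subgroup.

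The same flare raises the reference dose of a participant who was already on OCS. Protocol 8.1.1 encourages investigators, where medically appropriate, to return treatment to its pre-flare level. The event is then unfavourable in the primary endpoint but, once resolved, favourable in the OCS endpoints.

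The rule that therapy must be unchanged for 4 weeks before a flare does not screen these events out, because inclusion 5 already supplies 4 stable weeks before the first dose. No visible rule removes flare-driven OCS from the Weeks 0-4 mean. The visible derivation in SAP 6.2.1 selects by drug class and oral route, so a short oral course for another reason would act in the same way.

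At stake is whether the OCS results of a trial of about 15 participants describe a change from the dose at entry.

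**Working it through.** **Planning figure.** Protocol 9.2 and SAP 5 give a 95% CI of (0.07, 0.93) for 0.26 flares/year with N = 15. With a Wald interval on the log rate, SE = √(1/(15 × 0.26) + k/15), where k is the negative binomial dispersion. With k = 0 the interval is (0.10, 0.70). With k = 2.5, SE = 0.650 and the interval is (0.07, 0.93). The visible text does not give k, so the figure is plausible but not independently reproduced. It is used below only as a source of rates.

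**Windows.** Days 1-28 and days 337-364 after first dose are 28 days each, and SAP 6.2.1.1 divides each sum by 28.

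**Inflation of the reference.** An extra dose of a mg/day on t days adds I = a × t / 28 to the Weeks 0-4 mean. If maintenance is d and the participant is back at d in Weeks 48-52, the change is −I and the percentage change is −100 × I / (d + I). This reaches −50% only if d ≤ I. The increments and durations below are illustrative, except +10 mg for 5 days, which is the minimum in the flare definition.

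| Extra OCS in Weeks 0-4 | I (mg/day) | d = 5 mg | d = 10 mg | False ≥50% response if d is at most |
|---|---|---|---|---|
| +10 mg × 5 days | 1.79 | −26.3% | −15.2% | 1.79 mg/day |
| +10 mg × 14 days | 5.0 | −50.0% | −33.3% | 5 mg/day |
| +10 mg × 21 days | 7.5 | −60.0% | −42.9% | 7.5 mg/day |

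Against the Day 1 dose, the same participant shows a change of 0 in every row.

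**Membership.** With d = 0 and the minimum OCS flare, the Weeks 0-4 mean is 10 × 5 / 28 = 1.79 mg/day. The participant enters the subgroup and, back at 0 mg, counts as a 100% reduction and as meeting the 7.5 mg threshold. On the Day 1 dose the participant is outside the subgroup.

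**Opposite direction.** Standard of care may be adjusted from Visit 3 (Protocol 4.1, 6.8), and Visit 3 has a ±7 day window (Protocol Table 1). Illustration: 10 mg halved for the last 7 days of the window gives (10 × 21 + 5 × 7) / 28 = 8.75 mg. Staying at 5 mg then reads as a 42.9% reduction when the reduction from entry is 50%.

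**Which endpoints.**

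| Endpoint | Reference affected | Membership affected |
|---|---|---|
| Change in mean daily dose | yes | yes |
| Reduction ≥50% | yes | yes |
| ≤7.5 mg, on OCS at baseline | no | yes |
| ≤7.5 mg, whole population | no | no |

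**How often.** Expected flares of any type in the first 28 days are 15 × rate × 28 / 365.25:
- 0.26/year: 0.30, with a chance of at least one of 1 − exp(−0.30), about 26%.
- 0.93/year (upper CI limit): 1.07, about 66%.
- 2/year: 2.30, about 90%. This assumes that the minimum flare history for entry carries on. Inclusion 3 counts any documented escalation, a looser definition than the trial's.

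**Weight of one participant.** If a member's response status flips, the percentage moves by 1/n, which is at least 1/15 = 6.7 points. If a participant is wrongly added as a responder to n members with x responders, it moves by (n − x) / (n(n + 1)). For example, with n = 8 and x = 4 (assumed) it goes from 50.0% to 55.6%.

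**The case against.** The best defence is that Weeks 0-4 is the protocol's own reference, set in advance. Therapy is stable for 4 weeks before the first dose and adjustable only from Visit 3, so the window should approximate the entry dose, and comparing two 28-day means is sensible. The plan also shows mean dose for every 4-week period. SAP 4.3.1 adds a whole-population estimand for the change in dose, which removes the membership problem there, though not the reference problem. Early flares are counted in the primary endpoint, so they are not hidden. All these endpoints are descriptive.

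Most of this stands, and it is why the protocol's reference should remain the main one. It does not answer the membership rule, which the visible protocol does not require.

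A reader might infer more than the documents support:
- That every OCS secondary endpoint is distorted. The two 7.5 mg endpoints use no reference value, and the whole-population one has no subgroup either.
- That any early flare produces a false 50% responder. At 10 mg maintenance, the minimum OCS flare gives −15.2%. Flares treated only with immunosuppressive or cytotoxic therapy add no OCS at all.
- That the baseline OCS covariate in the primary negative binomial model is contaminated by the outcome. Part of SAP 4.1.2 is redacted, so the covariate's window cannot be determined and no claim is made about it.

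**Conclusion.** The point holds as a limited defect. Post-treatment events can decide who is in a subgroup named for baseline status, which affects three of four OCS secondary endpoints. They can also move the reference in two of four. An early OCS-treated flare makes the later change look more favourable, while an early taper makes it look less so. The net direction is therefore not fixed.

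At the planning rate of 0.26/year the likeliest outcome is that no early flare occurs (about 74%), and then this mechanism does nothing. If the early rate is nearer the rate before entry, one or more affected participants become likely, and in a subgroup of at most 15 each one is visible in the result. These frequencies assume a constant Poisson rate and count flares of any type, so they overstate the number that raise OCS. No hypothesis test, power or sample size figure changes.

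**What to change.** Define membership of the baseline-OCS subgroup in SAP 4.3.1 to 4.3.3 from the Day 1 pre-treatment dose, using the row already in Table 4. State that a course started on Day 1 for a flare does not count, since SAP 6.2.2.1 treats flares from that date as on-treatment.

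Keep Weeks 0-4 as the reference for the main change and ≥50% summaries, as the protocol names it. Say how the 50% criterion is handled if a member's Weeks 0-4 mean is zero. Add supplementary summaries of both endpoints against the Day 1 dose, and enter the change in SAP 4.11.

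The cost is SAP wording, one extra set of tables and possibly a slightly smaller subgroup. No new data are needed: concomitant medication is collected from Visit 2 (Protocol Table 1), and medication in use at enrolment must be recorded (Protocol 6.8). Replacing the Weeks 0-4 reference outright would change a protocol-named endpoint in an open-label trial, and the size of the problem does not call for it.
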